**STATEMENT OF COMPLIANCE**

The trial will be carried out in accordance with International Conference on Harmonisation Good Clinical Practice (ICH GCP E6 (R2)).

The protocol, informed consent form(s), recruitment materials, and all participant materials will be submitted to the Ethic Committee (EC) for review and approval. Approval of both the protocol and the consent form must be obtained before any participant is enrolled. Any amendment to the protocol will require review and approval by the IEC before the changes are implemented to the study. In addition, all changes to the consent form will be IEC-approved; a determination will be made regarding whether a new consent needs to be obtained from participants who provided consent, using a previously approved consent form.

The Principal Investigator will assure that no deviation from, or changes to the protocol will take place without prior agreement from sponsor, and documented approval from the IEC, except where necessary to eliminate an immediate hazard(s) to the trial participants. All personnel involved in the conduct of this study have completed ICH GCP Training.

**1 PROTOCOL SUMMARY**

**1.1 SYNOPSIS**

**Title:**

**“E-monitoring of pulmonary function in patients with Duchenne Muscular Dystrophy undergoing respiratory rehabilitation at home”. The controlled and observational 12-months study with prospective cohort design.**

**Short title: E-monitoring of pulmonary function in Patients with Duchenne Muscular Dystrophy (DMD).**

**\*Acronym: E-PULMoDMD**

**Abbreviations:**

DMD, Duchenne muscular dystrophy

BMI, body mass index

BS, Brooke scale

VS, Vignos scale

FVC, forced vital capacity

FEV1, forced expiratory volume in 1 second

PEF, peak expiratory flow

MEP, maximal expiratory pressure

MIP, Maximal inspiratory pressure

PUL, Performance of Upper Limb

**Study Description:**

The controlled and observational 12-months study with prospective cohort design and longitudinal data collection performs in paediatric patients with established diagnosis of DMD, at the Department of Allergy and Pulmonology Medical University of Gdansk, Poland.

The study includes 200 patients with DMD diagnosis confirmed by genetic testing, 7-17 years old (7  $\geq$  and  $<$ 18) at the study entry with the routine standardized a follow-up of up to 4 weeks, 12 weeks, 24 weeks and 12 months.

The study size is estimated at 200, with a dropout rate after the 12-month follow-up period being ca. 10% (N=180). The study consists of 4 arms: 3 actives and 1 control (each arm of n=50 participants; with dropout rate after 12 months ca.10%, n=45).

Duration of the project March 2021 - March 2025.

## 2 INTRODUCTION

Duchenne muscular dystrophy (DMD) is the most common and most severe muscular dystrophy recognized in childhood. DMD is a genetically determined, progressive, irreversible disease in which dystrophin dysfunction in skeletal and multiple organ muscles is fatal before the age of 20 years. Nowadays, multi-specialist care has resulted in an increase in patient survival by up to 10-25 years. However, the respiratory muscle failure is the most common cause of death [1,2], so assessment and treatment of respiratory system is one of the most important problems for DMD patients.

In the first years of life, the respiratory system of children with DMD is efficient and does not differ from that of healthy peers. From the age of 7 years, the parameters of lung function no longer increase, and between the ages of 10 to 12 years, when the child loses the ability to walk independently, the lung function rapidly deteriorates [3].

The basic tasks include the initiation of early monitoring of respiratory system functions. It is recommended that measurement of lung function is started from the age of 5 years [1,2,4]. Taking the measurement at such an early age is aimed at familiarizing and teaching the child about this type of systematic examination and determining the individual maximum parameters of lung function in each child. Thanks to systematic measurements, it is possible to detect any sharp deterioration as well as the moment when the decreasing lung function requires respiratory support, so-called non-invasive ventilation (NIV).

According to the standards, lung function is assessed by spirometry, which should be performed at least once a year, at least every 6 months after losing independent walking, and every 3 months after starting non-invasive ventilation [1,2].

The spirometry test assesses forced vital capacity (FVC), which is considered a marker of disease progression. An FVC value below 2.1 L is a rationale to start supporting the cough reflex, and below 1 L is an indication to start respiratory support, i.e. NIV [5,6,7,8,9,10].

Implementation of the above-mentioned tests often encounters difficulties which increase when the child loses independent walking. Additionally, during the COVID pandemic, which runs from March 2020 in Poland, spirometry was included in the procedures generating aerosols, i.e. high risk of SARS-CoV-2 virus transmission. Therefore, it has become necessary to look for other methods of measuring and monitoring lung function in children with DMD.

Because a major component of respiratory dysfunction seems to be decline of inspiratory muscle weakness [3,6] therefore also respiratory training and rehabilitation is recommended as one of the key elements of DMD patient care [1,3].

The time of the SARS-CoV-2 pandemic also makes it necessary to look for rehabilitation methods at home. The assumption of the exercises is the possibility of performing them independently, at home, without the assistance of a physiotherapist, and without the use of additional equipment.

Summary: Pulmonary rehabilitation is one of the key issues in DMD patient management. The combination of systematic home lung function measurement with home respiratory rehabilitation is an innovative project. It is a non-invasive test, and the measurement is intended to improve the quality of life of DMD patients.

### **3. AIMS, OBJECTIVE**

**Objectives:**

The primary objective of this study is to evaluate whether using home electronic device to monitoring pulmonary function and/or home telerehabilitation can slow the rate of progression pulmonary function in males with DMD compared to control group without using home e-device and telerehabilitation.

The second aim of this study is:

to investigate whether it is possible to monitor pulmonary function at home using an electronic spirometry system called AioCare in boys with DMD.

to assess the acceptance of telerehabilitation of respiratory system in this group of patients.

to assess the acceptance of electronic home monitoring of respiratory system in this group of patients.

to assessment of the quality of life of patients subjected to electronic monitoring and pulmonary rehabilitation vs. not subjected (validated questionnaires)

## 4. STUDY DESIGN

### 4.1 Overall design

The study consists of 4 arms: 3 actives and 1 control (figure 1).

ARM 1: Patients in arm 1 use electronic home device to measurements pulmonary function,

ARM 2: Patients in arm 2 use electronic home device to measurements pulmonary function, and perform telerehabilitation,

ARM 3: Patients in arm 3 perform telerehabilitation

CONTROL GROUP: Patients without home e-monitoring pulmonary function and telerehabilitation.

Enrolment of a patient to one of four groups (active or control) takes place after enrolment visit in random order.

As a part of the clinical trial, diagnostic examinations evaluating progression of the disease, pulmonary function tests will be performed periodically. The compliance, efficacy, accomplishment in all patients will be monitored by questionnaire during follow-up visits. The problems with investigate procedures (e-spirometry, telerehabilitation) and patients' personal well-being will be controlled using telemedicine technologies. Additional visits in the research center will be provided if any adverse events occur. This model will be continued for 12 months from the enrolment. After 4 weeks the first home e-monitoring pulmonary function and respiratory telerehabilitation efficiency analysis will be performed.

The study may be continued for 12 months or in case of negative impact of the intervention on patients' health and well-being, terminated with further patients monitoring

[figure not shown]

Figure 1. Study design

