## **8. STATISTICAL CONSIDERATIONS**

### **Sample size estimation**

Estimation of the sample size was based on the expected differences of the FVC between the groups with and without intervention. In the reference studies annual decline of FVC is varied between 6-11% (mean 8.5%). Assuming that telerehabilitation with using mobile spirometry can decrease this decline to 6% per year with standard deviation of 3% we estimated sample size for the study arms. Taking into account 80% power of the test, 5% significant level, the number of the subjects in the arm 1 (AioCare

device spirometry + telerehabilitation of the respiratory system) and control group equals 46 per group; finally 50 subjects per group were established. The same number of subjects were determined in the rest arms of the study (arm 2 – only mobile spirometry and arm 3 – only telerehabilitation).

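### Allocation is not stratified by walking status, although the protocol ties lung-function decline to it and records it before allocation: a cheap loss of precision and robustness, not a bias

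*Protocol*

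**What the plan says.** - **Allocation.** Under Overall design: "Enrolment of a patient to one of four groups (active or control) takes place after enrolment visit in random order". No stratum, block or minimisation factor is named there or elsewhere in the protocol.
- **Population.** The Study Description plans for "200 patients with DMD diagnosis confirmed by genetic testing, 7-17 years old", in four arms: "each arm of n=50 participants; with dropout rate after 12 months ca.10%, n=45". The inclusion criteria also require that a boy can perform spirometry and uses no breathing support.
- **Course of disease.** The Introduction has the growth of lung function ending at about age 7. It places the turn to steep decline later: "between the ages of 10 to 12 years, when the child loses the ability to walk independently, the lung function rapidly deteriorates". Loss of walking is thus the protocol's own marker of the turn.
- **Staging before allocation.** The Enrollment visit section has the Vignos scale scored in every boy and describes it as a staging scale centred on ambulatory function. Allocation comes after that visit, so the stage is known in time.
- **Planned effect.** The sample size section takes a control decline of 8.5% a year (6-11% across reference studies), 6% under the combined intervention, and an SD of 3%, which gives a difference of 2.5 points.
- **Analysis.** In the Statistical Analysis section, age and the Vignos and Brooke scores appear only in a regression on compliance with home spirometry.

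**The concern.** The primary objective is the rate of change of pulmonary function, and the Introduction links that rate to walking status. The trial mixes boys before and after the turn. If allocation ignores walking status, arms of 50 will differ in phase share by chance, and an arm with more boys past the turn would be expected to decline faster whatever the intervention does. The three active arms share one control, so an unlucky control arm moves all three contrasts together.

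This is a design matter. An analysis plan can adjust for walking status later, but it cannot stratify an allocation already made.

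**Working it through.** **1. The plan's own figure.** With difference 2.5, SD 3, 80% power and a two-sided 5% level (sidedness assumed):

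n per group = 2 × (1.96 + 0.842)² × 3² / 2.5² = 22.6, so 23 (24 with the t distribution).

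The stated 46 per group is not reproduced. It equals the total of two groups of 23, or the size per group if the SD were 3 × √2 = 4.24. That is a separate matter. It counts here only because, on the stated difference and SD, power is already 98.6% at 50 per arm and 97.7% at 45. The planned standard error of an arm difference is 3 × √(2/50) = 0.60 points.

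**2. Inputs the protocol does not give (assumed, with ranges).**
- Share p of boys in the earlier phase: 27% to 50%. Ages spread evenly over the eleven years 7-17 give 3/11 = 27% or 4/11 = 36%; 50% is the upper value.
- Gap D in annual FVC decline between the phases: 2.5 or 5 points. The value 5 is the width of the 6-11% range, but that range is across reference studies, not phases.

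**3. Size of chance imbalance.** The SD of the difference in phase share is √(2p(1−p)/50). The probabilities come from 100,000 simulated divisions of 200 boys into four arms of exactly 50.

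| p | SD of difference | One comparison ≥10 / ≥20 points | Any of three vs control ≥10 / ≥20 points |
|---|---|---|---|
| 27% | 8.9 points | 32% / 3% | 62% / 9% |
| 36% | 9.6 points | 35% / 5% | 67% / 12% |
| 50% | 10.0 points | 37% / 6% | 70% / 14% |

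In an arm of 50, ten points is 5 boys and twenty points is 10 boys. These results hold with arm sizes fixed at 50.

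**4. Effect on the FVC contrast.** Shift = imbalance × D.
- 10 points: 0.10 × 2.5 = 0.25 to 0.10 × 5 = 0.5 point.
- 20 points: 0.20 × 2.5 = 0.5 to 0.20 × 5 = 1.0 point, which is 20% to 40% of the planned 2.5.

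**5. Error rate.** These are simulated two-arm trials with p = 50%, 50 per arm, overall SD 3 and no adjustment. Over all allocations, type I error is 5.0% for either D. Among allocations with an imbalance of 20 points or more, it is about 13% (D = 2.5) or 46% (D = 5).

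**6. What stratifying and adjusting would gain.** If SD 3 is the overall SD, the residual SD after removing phase is √(9 − p(1−p)D²). At p = 50%:
- D = 2.5: √(9 − 1.56) = 2.73; standard error 2.73 × √(2/50) = 0.55.
- D = 5: √(9 − 6.25) = 1.66; standard error 1.66 × √(2/50) = 0.33.

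Both compare with 0.60 unadjusted.

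**The case against.** Four points can be made for the plan as it stands.

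- **The imbalance is already paid for.** If SD 3 is the overall SD, phase variation is part of it. At D = 5 and p = 50%, √(0.33² + (0.10 × 5)²) = 0.60, exactly the planned standard error. This stands. It is why the point concerns precision and not validity. If SD 3 is instead the SD within a phase, unadjusted power at 45 per arm would still be 95-96% (D = 2.5) or 86-89% (D = 5).
- **Adjustment could remove most of the shift, and an analysis plan that is not shown may specify it.** This stands too, and silence on adjustment is not counted against the protocol. But stratification has to be settled at allocation.
- **The sizes rest on assumptions.** The Introduction gives no rate per phase and no expected mix, and the eligibility criteria trim the most advanced boys. This stands; hence the ranges.
- **A 20-point imbalance is uncommon**, at 3-6% for any one comparison. The common case of about 10 points shifts the contrast by 0.25 to 0.5 point.

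Two stronger readings are tempting. A reader might infer that allocation is simple and unrestricted, so that arms would miss their target, with the smallest typically near 43. The protocol does not describe the method, and its statement of "each arm of n=50 participants" fits a restricted list at least as well. A reader might also infer that the FVC comparison is distorted or biased. Chance imbalance is random error with a correct overall error rate, and nothing in the protocol shows that it would be large in this trial.

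**Conclusion.** The point holds as a weakness in precision and robustness. The protocol describes a strong prognostic marker, enrols across it, measures it before allocation and does not use it. An imbalance of 10 points or more against control in at least one active arm is more likely than not (about 62-70%), and one of 20 points or more has a probability of about 9-14%. The larger imbalance would move the contrast by 0.5 to 1.0 point of 2.5.

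The probabilities rest on an assumed phase share of 27-50%. The shift rests on an assumed gap of 2.5-5 points in annual decline. The gain in standard error also requires that SD 3 is the overall SD. Overall type I error stays at 5%, and power on the protocol's own difference and SD is ample, so this is a worthwhile and inexpensive improvement and not a threat to validity.

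**What to change.** In Overall design, replace the allocation sentence with a statement that boys are allocated 1:1:1:1 from a computer-generated list in permuted blocks of varying size, stratified by walking status from the Vignos score at the enrolment visit. State which scores count as walking. Include that stratum as a factor in the between-arm FVC comparison; without it the precision gain in step 6 is not fully realised.

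The cost is slightly more work to prepare and run a list with two strata at one centre. No new measurement is needed.

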## 4.2 Investigate procedures

The presented project evaluates the measurement of lung function at home using an individual electronic spirometer called an AioCare [11] and home respiratory telerehabilitation.

### 4.2.1 Home e-spirometry

Home e-spirometry will be performed by AioCare system ((AioCare® spirometers, Healthup, Poland) [11]. The AioCare spirometer is a small, convenient device that can be used anywhere. The device enables systematic non-invasive monitoring of lung parameters (including FVC measurement) at home in children over 5 years of age. The child inhales and exhales forcefully through a mouthpiece with antibacterial and antiviral filters. The test results are sent from the AioCare spirometer via the AioCare application for iOS and Android (as used by all current smartphones). Communication between the AioCare spirometer and the application takes place via a Bluetooth 4.0 (BT LE) connection. The spirometry results are available to the practitioner in real time in the AIOCARE Doctor panel.

### 4.2.2 Home respiratory telerehabilitation

A module with exercises for training respiratory muscles, will be included in an additional smartphone application.

It will be a series of 4 exercises aimed at strengthening respiratory muscles, to be performed after the spirometry test; twice every day.

Participants will perform forced exhalation exercises with a relaxed epiglottis, exercises to improve the mechanics of the chest and the mobility of the shoulder girdle. The duration of the exercises is approximately 7 minutes. The exercise program will be recorded in the form of an instructional video.

## 4. STUDY POPULATION

### 4.1 Inclusion criteria

The study includes patients with signed informed consent, i.e. those who agree to participate in a clinical study and meet the inclusion criteria. The children will be enrolled in the study after their legal guardians read, agree to, and sign the informed consent form. All children older than 12 as well as adolescents will be enrolled in the study after signing the informed consent, as well. The subjects will be assessed for inclusion and exclusion criteria on first study visit after signing the informed consent.

Inclusion criteria are as follows: (1) male with DMD diagnosis based on current guidelines, the presence of typical clinical symptoms, genetic testing, and/or muscle biopsy results [1]. (2) male,  $\geq 7$  years and  $< 18$  years of age at time of enrollment in the study; (3) ability to perform spirometry; (4) do not use breathing support; and (5) stated willingness to comply with all study procedures and availability for the duration of the study.

### 4.2 Exclusion criteria

Autism

## 6. PARTICIPANT RECRUITMENT PROCESS

### 6.1 Recruitment Setting

In order to support the recruitment of patients the following actions will be undertaken:

#### I. Public study announcement and participant invitation

- preparation and distribution of the informational advertisements, fliers, and brochures
- preparation of the study website containing information for patients and their families
- establishment of contact and cooperation with patient's organizations throughout the country (such as "Parent Project DMD")
- other actions as outlined in the Recruitment strategies

#### II. Contacting potential participants

- answer any preliminary questions or doubts over a phone or internet communicator as suitable for the patient or guardian, point to the study website

### 6.2 Screening

Screening will take place at the study Site. Medical workup will include a visit to the nurse (measurements), interview and medical examination. Education on the study protocol. Signing the study consent form.

Every subject after giving the consent will be given one, unique screening number. The number will be used for identification of the subject for all procedures. In case a subject is screened more than once he will always have the same screening number.

The investigator agrees to complete a participant identification and enrolment log to permit easy identification of each participant during and after the study.

### **6.3 Informed Consent, Trial Records**

The study will be conducted in accordance with the protocol, with established ethical principles in the Helsinki Declaration, in line with the harmonized ICH Guidelines for Good Clinical Practice (GCP), Relevant BI Standard Operating Procedures (SOP), and other relevant recipes. Investigators and plant employees must follow these rules. Deviation from protocol, rules of ICH GCP or applicable law that will be considered "protocol deviation".

Standard medical care (prophylactic, diagnostic and treatment procedures) still remains responsibility of the patient's doctor and participants are required to attend neurologist, rehabilitation specialist and other specialist if indicated for supervision of musculoskeletal function in accordance with current DMD treatment guidelines.

The Investigator will obtain the written informed consent from the subject's parent(s) or guardian(s) prior to any study-specific procedures.

Each subject's parent(s) or guardian(s) will receive an explanation of the nature and purposes of the study from the Investigator or designee.

Time will be given to the parent(s)/guardian(s) to ask questions and make their decision on whether they would like for their child to participate.

The Investigator or designee will ensure the study is appropriate for the subject.

Subjects are considered to be enrolled in the study at the time written informed consent is obtained.

#### **6.3.1 Consent Process**

Informed consent is a process that is initiated prior to the individual's agreeing to participate in the study and continues throughout the individual's study participation. Consent forms will be IEC-approved, and the subject's parent(s) or guardian(s) and participant will be asked to read and review the document. The investigator will explain the research study and answer any questions that may arise. A verbal explanation will be provided in terms suited to the participant's comprehension of the purposes, procedures, and potential risks of the study and of their rights as research participants. The participants should have the opportunity to discuss the study with their family or surrogates or think about it prior to agreeing to participate. The informed consent process will be conducted and documented in the source document (including the date), and the form signed, before the participant undergoes any study-specific procedures. The rights and welfare of the participants will be protected by emphasizing to them that the quality of their medical care will not be adversely affected if they decline to participate in this study.

The subject's parent(s) or guardian(s) will be asked if s/he understands that the study is for research purposes only and that it may not provide any benefit to the subject and that the subject is free to withdraw from the study at any time without prejudice. Each subject's parent(s) or guardian(s) will be

required to sign a study ICF before any procedures are performed for the study; both parents or guardians will sign the ICF in jurisdictions where this is required.

If applicable, the assent of the child himself will also be obtained, if possible, in writing per individual where a child is intellectually capable of assenting (and in accordance with local regulations: according to Art. 25 (in connection with Article 37h (1) (1) of the PF), if a minor is 16 or under 16 and is able to expressly express his opinion on his participation in the experiment, his consent is also required. At any time, the researcher is obliged to take into account the wishes of the minor (able to express an opinion) regarding the refusal to participate in the study or withdrawal from the study.), and with the permission of the parent(s)/guardian(s).

The Investigator or designee will obtain ICF in accordance with the principles outlined in the current version of the Declaration of Helsinki. Informed Consent Forms must be dated and signed by the Investigator or designee and the subject's legal representative(s) and the original signed consent form must be kept by the Investigator in the study subject's file.

"Legal representative" means an individual whom a judicial or other body authorized under applicable law to consent on behalf of a prospective study subject to the subject's participation in the procedure(s) involved in the research. The Study Monitor will ensure that the ICF has been signed by the subject's legal representative(s). The study subject's legal representative(s) will receive a copy of the signed consent form. Consent will be a continuing process; investigator will foster a continuous dialogue with participants and inform them of anything new related to the trial.

